

1. To demonstrate that vaccination with aQIV elicits an immune response that is not inferior to that of an aTIV containing the same virus strains as the US licensed adjuvanted influenza vaccine (Fluad, aTIV-1), and an aTIV containing the alternate B strain (aTIV-2) among adults <math>\geq</math> 65 years of age.

2. To assess the immunogenicity of aQIV in adults <math>\geq</math> 65 years of age, based on the CBER (Center for Biologics Evaluation and Research) recommendations.

		
Secondary Immunogenicity Objectives:		
The secondary objectives of the study are to assess the following, among adults aged $\geq$ 65 years: 

1. To characterize the immunogenicity of aQIV, the aTIV-1 containing the same virus strains as the US licensed adjuvanted trivalent influenza vaccine, and the aTIV-2 containing the alternate B strain, by hemagglutination inhibition (HI).

2. To demonstrate the immunological superiority of aQIV compared to aTIV-1 and aTIV-2 for the B strain that is not included in each TIV vaccine separately;

		
Secondary Safety Objective:		

1. To assess safety and tolerability of aQIV, aTIV-1, and aTIV-2 among adults <math>\geq</math> 65 years of age.

		

Name of Sponsor: Seqirus Inc.	Protocol number: V118_20	Generic name of study vaccine(s): MF59-adjuvanted Quadrivalent Subunit Inactivated Egg-derived Influenza Vaccine (aQIV); Licensed MF59-adjuvanted Trivalent Subunit Inactivated Egg-derived Influenza Vaccine (aTIV-1); MF59-adjuvanted Trivalent Subunit Inactivated Egg-derived Influenza Vaccine Containing the Alternate B Strain (aTIV-2).
Exploratory Immunogenicity Objectives:		

1. To explore the association between HI immune response after administration of aQIV or the aTIV-1, containing the same virus strains as the US-licensed adjuvanted trivalent influenza vaccine, and the aTIV-2 containing the alternate B strain by baseline characteristics.

2. Characterization of the immunogenicity of aQIV using other immunological assays (e.g., virus neutralization [MN] or anti-neuraminidase antibody assays may be performed).

		
Both exploratory objectives may be performed using either homologous or heterologous strains, or both.		

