Name of Sponsor: Seqirus Inc.	Protocol number: V118_20	Generic name of study vaccine(s): MF59-adjuvanted Quadrivalent Subunit Inactivated Egg-derived Influenza Vaccine (aQIV); Licensed MF59-adjuvanted Trivalent Subunit Inactivated Egg-derived Influenza Vaccine (aTIV-1); MF59-adjuvanted Trivalent Subunit Inactivated Egg-derived Influenza Vaccine Containing the Alternate B Strain (aTIV-2).
Secondary Immunogenicity Endpoints:		
Characterization of immunogenicity of aQIV, aTIV-1 and aTIV-2:		
The measures of immunogenicity of aQIV, aTIV-1 and aTIV-2 will be assessed in terms of HI antibodies. Serum HI antibody titers against the 4 influenza vaccine strains will be used to calculate:		

• GMT: Geometric mean of HI titers on Day 1 and Day 22;

• GMR: The geometric mean of the fold increase of post- vaccination HI titer over the pre-vaccination HI titer (Day 22/Day 1);

• The percentage of subjects with a titer <math>\geq 1:40</math> at Day 1 and Day 22;

• SCR: the percentage of subjects with either a prevaccination HI titer <math>< 1:10</math> and a postvaccination HI titer <math>\geq 1:40</math> or a prevaccination titer <math>\geq 1:10</math> and a <math>\geq 4</math>-fold increase in postvaccination titer on Day 22.

		
Superiority of immunologic response for aQIV vs aTIV:		
Superiority of aQIV over aTIV-1 and aTIV-2 for antibody response to the alternate B strain will be assessed using the GMT ratio (aTIV/aQIV) and difference in SCR (aTIV – aQIV) at Day 22. Point estimates and 95% confidence limits will be obtained as described for the primary endpoint. Superiority will be declared if the upper limit of the two-sided 95% CI for the difference in SCR (aTIV – aQIV) is $< 0$ and the upper limit of the two sided 95% CI for the GMT ratio (aTIV/aQIV) is $< 1$ for both B strains.		
Interim Analysis: An interim analysis is not planned for this study.		
Data Monitoring Committee: An independent Data Monitoring Committee will not be utilized for the study.		

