### 2.2 Secondary Immunogenicity Objectives

The secondary immunogenicity objectives of the study are to assess the following, among adults aged  $\geq 65$  years:

1. To characterize the immunogenicity of aQIV, the aTIV-1 containing the same virus strains as the US licensed adjuvanted trivalent influenza vaccine, and the aTIV-2 containing the alternate B strain, by hemagglutination inhibition (HI).
2. To demonstrate the immunological superiority of aQIV compared to aTIV-1 and aTIV-2 for the B strain that is not included in each TIV vaccine separately.

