### 8.1.2 Secondary Immunogenicity Endpoints

- The measures of immunogenicity of aQIV, aTIV-1 and aTIV-2 used for Secondary objective 1 as determined by the HI assay against homologous strains at Day 1 and 22 (unless indicated otherwise), include the following:
  - GMT: Geometric mean of HI titers on Day 1 and Day 22
  - Geometric mean ratio (GMR)\*: The geometric mean of the fold increase of post- vaccination HI titer over the pre-vaccination HI titer (Day 22/Day 1)
  - The percentage of subjects with a titer  $\geq 40$  at Day 1 and Day 22
  - SCR: the percentage of subjects with either a prevaccination HI titer  $< 1:10$  and a postvaccination HI titer  $\geq 1:40$  or a prevaccination titer  $\geq 1:10$  and a  $\geq 4$ -fold increase in postvaccination titer on Day 22
- For Secondary objective 2, the immunologic superiority of HI antibody responses for the alternate B strain (the influenza B strain included in the aQIV but not in the aTIV formulation) in aQIV will be assessed for each aTIV separately, using the endpoints of the ratio of HI GMT and the difference of SCR for each B virus strain 21 days after vaccination.

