### **8.2.2 Success Criteria for Secondary Objectives**

#### **8.2.2.1 Success Criteria for Secondary Immunogenicity Endpoints**

There are no specific success criteria for the assessment of immunoassay results (first secondary objective).

Superiority of aQIV versus aTIV-1 and aTIV-2 for the alternate B strain will be assessed using the GMT ratio ( $GMT_{aTIV}/GMT_{aQIV}$ ) and difference in SCR ( $SCR_{aTIV} - SCR_{aQIV}$ ) at Day 22. Point estimates and two-sided 95% CIs will be obtained as described for the primary endpoint. Superiority will be declared if the upper limit of the two-sided 95% CI for the difference in  $SCR_{aTIV} - SCR_{aQIV}$  is  $< 0\%$ , and the upper limit of the two-sided 95% CI for the GMT ratio ( $GMT_{aTIV}/GMT_{aQIV}$ ) is  $< 1$  for both B strains.

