#### 8.4.3.3.1 Statistical Hypotheses

No statistical testing will be performed for the first secondary immunogenicity objectives.

*Superiority of B-strain response (geometric mean titers and proportions of subjects with seroconversion):*

For superiority of aQIV B strain response, the hypotheses are that immunologically aQIV is superior compared to aTIV-1 and aTIV-2 for the B strain that is not included in each TIV vaccine separately. In mathematical form, these are:

$$H_{0k}^{(GMT)}: GMTr_k \geq 1 \text{ vs } H_{1k}^{(GMT)} GMTr_k < 1 \text{ for } k=1,2$$

and

$$H_{0k}^{(SCR)}: D_k \geq 0 \text{ vs } H_{1k}^{(SCR)} D_k < 0 \text{ for } k=1,2$$

where  $GMTr_k$  is the ratio of geometric mean titer  $GMT_{aTIV-k}/GMT_{aQIV}$  of mismatched B strain for  $k=1, 2$ , and  $D_k$  is the differences  $\pi_{aTIV-k} - \pi_{aQIV}$  of mismatched B strain Day 22 SCR differences for  $k=1,2$ .

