11.2 Analysis of Secondary Objectives

11.2.1 Analysis of Secondary Immunogenicity Objective(s)

Characterization of immunogenicity of aQIV, aTIV-1 and aTIV-2:

The measures of immunogenicity of aQIV, aTIV-1 and aTIV-2 will be assessed in terms of HI antibodies. Serum HI antibody titers against the 4 influenza vaccine strains will be used to calculate:

- GMT: Geometric mean of HI titers on Day 1 and Day 22

- GMR: The geometric mean of the fold increase of post-vaccination HI titer over the pre-vaccination HI titer (Day 22/Day 1)
- The percentage of subjects with a titer $\geq 1:40$ at Day 1 and Day 22
- SCR: the percentage of subjects with either a pre-vaccination HI titer $< 1:10$ and a post-vaccination HI titer $\geq 1:40$ or a pre-vaccination titer $\geq 1:10$ and a ≥ 4 -fold increase in post-vaccination titer on Day 22

Superiority of immunologic response for aQIV vs aTIV:

Superiority of aQIV over aTIV-1 and aTIV-2 for antibody response to the alternate B strain will be assessed using the adjusted GMT ratio (GMT_{aTIV}/GMT_{aQIV}) and difference in SCR ($SCR_{aTIV} - SCR_{aQIV}$) at Day 22. Point estimates and 95% confidence limits will be obtained as described for the primary endpoint. Superiority will be declared if the upper limit of the two-sided 95% CI for the difference in ($SCR_{aTIV} - SCR_{aQIV}$) is < 0 and the upper limit of the two-sided 95% CI for the GMT ratio (GMT_{aTIV}/GMT_{aQIV}) is < 1 for both B strains.

The same GLM as was used for the primary analysis will be used to determine the adjusted GMT ratio for assessing superiority.

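### The B-strain superiority objective is worded for each aTIV separately, but the only declaration rule is joint; a fixed sequence would add a single-comparator claim at no cost in error or in power for both

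*Protocol*

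**What the plan says.** The objective (Protocol Synopsis and 2.2; SAP 2.2.1) reads: "To demonstrate the immunological superiority of aQIV compared to aTIV-1 and aTIV-2 for the B strain that is not included in each TIV vaccine separately". Protocol 8.1.2 says that the alternate B strain "in aQIV will be assessed for each aTIV separately, using the endpoints of the ratio of HI GMT and the difference of SCR", and SAP 2.2.2 agrees. Protocol 8.4.3.3.1 and SAP 11.2.2 state the null hypotheses for GMT and for SCR with an index k = 1, 2, one pair for each aTIV.

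The declaration rule is a single one. In Protocol 8.2.2.1 it begins "Superiority will be declared if the upper limit of the two-sided 95% CI for the difference in" SCR, requires that limit to be below 0%, adds that the upper limit for the GMT ratio must be below 1, and closes with the condition that this hold "for both B strains". The same rule stands in the Synopsis, where the GMT half is met if the upper limit of the "two sided 95% CI for the GMT ratio (aTIV/aQIV) is $< 1$ for both B strains", and in Protocol 8.4.3.3, and SAP 2.4.2.1 and 11.2.1.

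No section says what may be declared if both criteria are met against one aTIV but not the other. SAP 8.4 states that there is no multiplicity adjustment. No test order is given for the two contrasts.

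**The concern.** By the vaccine composition tables (Protocol 6.1), aTIV-1 lacks B/Yamagata and aTIV-2 lacks B/Victoria. The stated aim (Protocol 1.2) is to show that the additional B strain elicits a response. Relative to the licensed vaccine, aTIV-1, that strain is B/Yamagata, so aQIV against aTIV-1 for B/Yamagata is the contrast closest to the aim.

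Under the joint rule, aQIV could pass both criteria in that contrast, miss one criterion against aTIV-2 for B/Victoria, and leave the sponsor with no declaration. A claim against aTIV-1 alone would then fall outside the prespecified rule and be post hoc. What is at stake is one secondary claim, not the study's success or the validity of any test.

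**Working it through.** **1. Calibration on the plan's own figures.** Inputs from Protocol 8.5 and Table 8.5-1: B-strain SCR 40%, 800 aQIV and 400 aTIV evaluable subjects, margin 10%, one-sided alpha 0.025, SD of log_e titer 1.2.

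- Noninferiority on SCR, Wald: SE = sqrt(0.24 × (1/800 + 1/400)) = 0.0300; power = Φ(0.10/0.0300 − 1.96) = 91.5%. A score test with restricted maximum-likelihood variance gives the plan's 91.29%.
- Noninferiority on GMT ratio, B strains: 99.98%, as stated.
- Overall: 0.8242 × 0.9996 = 82.39%, as stated.

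The inputs therefore reproduce the plan's numbers, and no stated figure is disputed. The plan gives no power for superiority.

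**2. Superiority on SCR, one contrast.** The SCR in an aTIV arm for the B strain it lacks, q, is not in the documents, so it is varied. Power = Φ((0.40 − q)/sqrt(0.24/800 + q(1 − q)/400) − 1.96).

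| q | SE | Power | 1 − power |
|---|---|---|---|
| 20% | 0.0265 | >99.9% | <0.1% |
| 28% | 0.0284 | 98.9% | 1.1% |
| 30% | 0.0287 | 93.6% | 6.4% |
| 32% | 0.0291 | 78.6% | 21.4% |
| 34% | 0.0293 | 53.4% | 46.6% |

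If the aTIV-1 contrast is near certain (q = 20% for B/Yamagata), the last column, read at the aTIV-2 value of q for B/Victoria, is the share of trials in which aTIV-1 is beaten but nothing is declared. If q is 28% in both arms, the chance of passing both on SCR is 0.9885² = 97.7% under independence, so the joint rule costs little there.

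**3. Superiority on GMT, one contrast.** SE = 1.2 × sqrt(1/800 + 1/400) = 0.0735. Power = Φ(|ln r|/0.0735 − 1.96), which is 85.9% at a true ratio r of 0.80 and 59.9% at 0.85. These ratios are also assumptions.

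**4. Error under three rules.** Let claim k be superiority over aTIV-k on both measures.

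- Joint rule: a false declaration requires rejecting at least one true null, so its probability is at most 0.025.
- Two unadjusted separate claims: up to 1 − 0.975² = 0.0494 under independence, or 0.05 by Bonferroni.
- Fixed sequence, claim 1 then claim 2: if claim 1 is false, any false declaration needs a wrong pass at step 1, at most 0.025. If claim 1 is true and claim 2 false, it needs a wrong pass at step 2, at most 0.025. The familywise error is at most 0.025.

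**5. Power under the fixed sequence.** Both claims are declared exactly when both contrasts pass, which is the joint rule's event, so that probability is identical. The only added outcome is a declaration for aTIV-1 alone.

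**The case against.** The joint rule can be defended on several grounds, and most of them stand.

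- **Wording.** The objective joins the comparators with "and", and "separately" can mean that each aTIV is compared, unpooled, on its own missing strain. That contrasts with the A strains, for which Protocol 8.1.1.1 pools the two aTIV groups. Hypotheses per comparator with a joint success rule form an ordinary intersection-union test. A reader might infer that the rule contradicts the objective; the documents do not support that.
- **Consistency.** The rule has the same sense wherever it appears, mirrors the all-or-nothing logic of the co-primary endpoints, and controls error without adjustment. A reader might infer an inflated error rate; the reverse is true, since the only risk is a forgone claim.
- **The remedy keeps a dependence.** Under a fixed sequence, superiority over aTIV-2 still cannot be declared if aTIV-1 misses. Neither document ranks the contrasts.
- **The size is assumed.** The larger losses need a marginal aTIV-2 contrast beside a near-certain aTIV-1 contrast, and nothing in the documents supports that asymmetry. The calculation uses Wald intervals, whereas Protocol 8.4.2.2.3 and SAP 11.1.4 specify exact ones.
- **Reporting.** Estimates and 95% limits for each contrast are produced in any case.

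What these points do not remove is that the fixed sequence permits every declaration the joint rule permits, plus one, at the same error bound. Reported intervals do not replace a prespecified claim.

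**Conclusion.** The point holds as a low-severity improvement to a secondary objective. The current rule is valid and conservative, but it leaves no formal declaration against a single comparator, which the wording of the objective, endpoint and hypotheses allows.

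The gain ranges from negligible (about 1% of trials at an aTIV-2 SCR of 28%) to large (about 47% at 34%). It is conditional on aQIV SCR of 40%, a near-certain aTIV-1 contrast, the SCR limb only and a Wald approximation. If the aTIV-1 contrast is near certain on both measures, adding the GMT limb can only raise these shares.

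It would be too strong to read those percentages as expected losses in this trial, because the plan supplies no rate for a missing strain. It would also be too strong to say that a clear aTIV-1 result would be lost: it would be reported, only without a prespecified claim. Study success rests on the co-primary objectives (Protocol 8.2, SAP 2.4) and is unaffected.

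**What to change.** Before unblinding, replace the joint rule with a fixed sequence at one-sided 0.025:

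1. Declare superiority over aTIV-1 for B/Yamagata if the upper limits of the two-sided 95% CIs are below 0 for the SCR difference (aTIV − aQIV) and below 1 for the GMT ratio (aTIV/aQIV).
2. Only if step 1 passes, declare superiority over aTIV-2 for B/Victoria on the same two criteria.

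Use one wording in the Synopsis, Protocol 8.2.2.1 and 8.4.3.3, and SAP 2.4.2.1 and 11.2.1. Putting the licensed comparator first is a sponsor decision and should be recorded as one. Deleting the requirement for both strains without an order or an alpha split is not equivalent, because the familywise bound would rise to about 0.05.

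If only a joint claim is wanted, keep the rule and say in the objective and endpoint that the claim is joint.

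The cost is wording: no added subjects, data or alpha. The SAP is to be final before unblinding (Protocol 8.4), and SAP section 14 already foresees a protocol update that could carry the change.

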**Table 1: Time and Events Table**

Assessment	Clinic Visit 1	Reminder Phone Call	Safety Phone Call	Clinic Visit 2	Safety Phone Call	Safety Phone Call 
	Day 1	Day 3 (-1 to + 1 days)	Day 15 (-3 to + 3 days)	Day 22 (-3 to + 3 days)	Day 91 (-7 to +7 days)	Day 181 (-14 to + 14 days)
EDC Visit no:	1	2	3	4	5	6
Informed consent 	✓					
Demographics and influenza vaccination history 	✓					
Medical history and baseline medication use 	✓					
Physical examination 	✓			✓		
Oral temperature, vital signs, height, weight 	✓					
Review of eligibility criteria 	✓					
Blood sample for immunogenicity testing 	✓			✓		
Vaccination 	✓					
Provision of study supplies and instructions 	✓					
Subject Diary Card reviewed and collected				✓		
Telephone contact 		✓	✓		✓	✓
Assess influenza-like illness (if applicable) 	↔					
Assess all unsolicited adverse events and concomitant medications 			✓	✓		
Assess SAEs, NOCDs, withdrawal AEs, AESIs & associated medications	↔			✓		

1. The invitation to participate and the informed consent process must be conducted within 10 days before the day of vaccination (Day 1)
2. Confirm that patient has had the opportunity to ask questions and consent form(s) are signed prior to any V118\_20 procedures being performed.
3. Procedure to be performed prior to vaccination. All eligibility criteria must be met before any study procedures (eg., blood sampling) can be performed.
4. Physical examination must be performed by a qualified health care practitioner in accordance with local regulations and licensing requirements designated within the Site Responsibility Delegation Log.
5. Vaccination should occur only after the pre-dose blood sample collected.
6. After vaccination, the subject will remain under medical supervision for at least 30 minutes and observed for local and systemic AE and unsolicited AEs. A body temperature measurement (preferably oral) will be taken.
7. A Diary Card, thermometer and ruler will be dispensed at Day 1. Subject will receive instruction on diary completion and thermometer and ruler use.
8. On Day 1 approximately 6 hours after the vaccination or prior to going to bed at the latest, and daily thereafter through Day 7, solicited local and systemic adverse events including other adverse events (i.e., body temperature measurements and use of analgesics/antipyretics) will be reported daily by the subject in the Diary Card.
9. The reminder call at Day 3 will be made by site staff to remind the subject to complete the Diary Card. In the safety calls at Day 15, Day 91 and day 181, subjects will be interviewed by site staff using a scripted interview for collection of safety data. These safety data will be collected in source documents by the individuals performing the interviews.
10. The subject will be asked to contact the site staff if the subject experiences ILI symptomsa during the interval between Day 1 and Day 22 (i.e., up to and including the day of the Day 22 blood sample). The subject should visit the site within 3 days of the onset of the ILI in order for a nasopharyngeal swab sample to be taken, however samples will be accepted if collected up to 6 days following the day of ILI onset. The sample will be sent to the central laboratory for RT-PCR analysis.
- adefined as at least one of the following respiratory symptoms: sore throat, cough, sputum production, wheezing, or difficulty breathing; concurrently with at least one of the following systemic symptoms: oral temperature of >37.2°C/ 99°F, chills, tiredness, headache, or myalgia.
11. All adverse events through the day 22 visit, and medications used to treat them.
12. Any subject who terminates the study prematurely after receiving a vaccination should have a termination visit/call ([Section 5.5.1](#)).

## LIST OF ABBREVIATIONS

AE	Adverse Event
AESI	Adverse Event of Special Interest
CBER	Center for Biologics Evaluation and Research
CDC	Centers for Disease Control and Prevention
CI	Confidence Interval
CRF	Case Report Form
CRO	Contract Research Organization
CSR	Clinical Study Report
DCF	Data Clarification Form
DMC	Data Monitoring Committee
EC	Ethics Committee
EDC	Electronic Data Capture
EMA	European Medicines Agency
FAS	Full Analysis Set
FDA	United States Food and Drug Administration
GCP	Good Clinical Practices
GMR	Geometric Mean Ratio
GMT	Geometric Mean Titer
GMTr	Geometric Mean Titer Ratio
HA	Hemagglutinin
HI	Hemagglutination Inhibition

---

HIPAA	Health Insurance Portability and Accountability Act
IB	Investigator's Brochure
ICF	Informed Consent Form
ICH	International Council (previously Conference) on Harmonisation of Technical Requirements for Pharmaceuticals for Human Use
ILI	Influenza-Like Illness
IM	Intramuscular
IRB	Institutional Review Board
IRT	Interactive Response Technology
MedDRA	Medical Dictionary for Regulatory Activities
MN	Microneutralization
NA	Neuraminidase
NOCD	New Onset of Chronic Disease
NP	Nasopharyngeal
PCR	Polymerase Chain Reaction
PP	Per Protocol
PPS	Per Protocol Set
PV	Pharmacovigilance
aQIV	Adjuvanted Quadrivalent Influenza Vaccine
QIV	Quadrivalent Influenza Vaccine
RT-PCR	Reverse Transcriptase Polymerase Chain Reaction
SAE	Serious Adverse Event
SAP	Statistical Analysis Plan

---

SC	Seroconversion
SCR	Seroconversion Rate
SDA	Source Data Agreement
SOC	System Organ Class
SOP	Standard Operating Procedure
aTIV	Adjuvanted Trivalent Influenza Vaccine
TIV	Trivalent Influenza Vaccine
WHO	World Health Organization
VSAE	Vaccine Serious Adverse Event

## 1. BACKGROUND AND RATIONALE

### 1.1 Background

Influenza is an infectious disease caused by the influenza virus, an orthomyxovirus with two clinically relevant types (types A and B). The disease is characterized by the abrupt onset of respiratory and systemic symptoms, such as fever, myalgia, headache, severe malaise, nonproductive cough, sore throat, and rhinitis (Temte and Prunuske, 2010), and occurs in epidemics throughout the northern and southern hemisphere winter months in temperate climates. In general, influenza is resolved within two to seven days, although symptoms of cough and malaise may be prolonged. However, for some people, notably older adults and those with chronic diseases (such as pulmonary or circulatory disorders, metabolic disorders such as diabetes mellitus, renal dysfunction, or immunosuppression), influenza can exacerbate underlying medical conditions and/or lead to secondary viral or bacterial pneumonia (Rothberg et al., 2008; Fiore et al., 2009). During influenza epidemics, there is increased mortality among older adults (age > 65 years) and people with chronic diseases, as well as an increase in morbidity and hospitalization because of influenza-associated complications (Fiore et al. 2009; Monto 2008).

The ability of vaccination to prevent influenza in older adults appears to be lower compared with younger adults (Osterholm, Kelley et al., 2012; Beyer, McElhaney et al., 2013), possibly because of a less robust immune response after influenza vaccination (Goodwin, Viboud et al., 2006; Sasaki, Sullivan et al., 2011). One way to increase immunogenicity of influenza vaccines is through the use of adjuvants, such as the squalene and water emulsion adjuvant, MF59. Fluad, Seqirus' trivalent seasonal influenza vaccine adjuvanted with MF59, has been licensed for use in Europe since 1997 and in the US since 2015. It has been shown to generate significantly higher geometric mean hemagglutination inhibition (HI) titers and rates of seroconversion than a non-adjuvanted trivalent influenza vaccine comparator in elderly subjects (Frey et al., 2014).

Trivalent influenza vaccines contain just one B strain antigen. Influenza type B viruses, however, have separated into two distinct genetic lineages since 1985, Yamagata and Victoria (Rota et al., 1990). B strains from either lineage may circulate simultaneously (Ambrose and Levin, 2012) and cause infection, and mismatch may occur between circulating B strains and the strain contained in a trivalent vaccine (Lo, Chuang et al., 2013). On average, influenza B strain accounts for approximately 25% of positive specimens in the US. Mismatches between the B strain in a trivalent vaccine and the circulating strain occur in approximately 5 out of every 10 influenza seasons (Belshe, 2010). To overcome this, several quadrivalent inactivated influenza vaccines are now licensed in the US, containing representative vaccine strains for both B-strain lineages, as well as the H1N1 and H3N2 A subtypes.

